### **4.2 Exclusion Criteria**

- Subjects enrolled in study protocol HSR 210184 no longer alive, able or willing to complete follow up visit at 1 year after enrollment.
- Any woman who is currently pregnant, or who could be pregnant due to menses history/pregnancy test

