## 6.0 STATISTICAL CONSIDERATIONS

### 6.1 Statistical analysis

All subjects who received one dose of study drug will be included in the safety analysis. Each primary and secondary efficacy outcome measure will be analyzed for the intent-to-treat (ITT) and evaluable population. The intent-to-treat principle is that participants will be analyzed in the groups to which they were randomized, regardless of whether they received the randomized study medication.

Data will be summarized as frequency with percentage for categorical clinical variables, and as mean  $\pm$  standard deviation or median with interquartile range for continuous variables. The difference between dupilumab and placebo arms will be tested with Chi-square for categorical measures (e.g., the primary endpoint) and two-sample t-test or Wilcoxon rank sum test for continuous measures (e.g., biomarkers). Due to the relatively small sample size in the study, the adjusted treatment effect of dupilumab will be estimated exploratively in generalized linear regression for the primary and secondary outcomes to account for the potential impact of patient characteristics (e.g., age, sex, race and co-morbidities) and baseline biomarker measures. Data transformation will be considered for the outcomes with skewed distribution. The difference in the biomarker measures at the follow-up visit and their changes from baseline between dupilumab and placebo groups will also be assessed. Since this is intended to be an early stage, proof of concept study for which the primary goal is to inform future trials rather than to perform formal hypothesis testing, no multiplicity adjustment is planned.

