### 6.2 Sample Size justification

Under the protocol HSR 210184, we conducted a randomized double-blind placebo-controlled trial assessing the safety and efficacy of dupilumab for treating hospitalized patients with acute moderate to severe COVID-19, which was designed as an early stage (Phase IIa) and proof of concept study. A total of 40 patients were enrolled from June 23, 2021 through November 180 11, 2021 in the Phase IIa study, and 7 of them died by Day 60. The sample size of 40 in the original Phase II study were determined largely based on the feasibility with a primary goal to collection reliable data and obtain sufficient evidence for future trials. The current proposed study is an extension of the original Phase IIa study under the HSR 210184, to assess the post recovery of remaining 33 patients from COVID-19 with respect to pulmonary function testing (PFT), pulmonary imaging, immune biomarkers and symptoms at one-year follow-up. All data will be collected at a single visit, 1 year (i.e.,  $365 \pm 90$  days) after initial enrollment in the remaining 33 parents from the study HSR 210184. Formal sample size estimation and power analysis is not performed due to the pilot nature of this proposed follow-up study.

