Since this is a small trial, simple randomization procedure may result by chance in the compositions of the study arms being markedly different with respect to factors that may affect the outcome measures in the trial, or markedly unequal numbers of participants may be recruited to each arm. Further, disease severity measured by the required oxygen $\leq 15\text{L}$ or $> 15\text{L}$ by nasal cannula may impact on the outcomes differentially. Thus, to ensure the

balance of treatment allocation in disease severity, the blocked randomization with block size of 4 will be performed, stratifying based on disease severity: patients who are on 15L or less of oxygen by nasal cannula (severity group A) and those requiring more than 15L of oxygen by nasal cannula including any noninvasive ventilation measures (severity group B). Thus, separate randomization lists will be generated for mild and severe patients, using the Proc Plan procedure in SAS, and the complete randomization lists will be sent to UVA Pharmacy only to ensure the blindness for others.

Example list for mild disease group:

Disease Severity	Order	Treatment Arm	Subject Initial	SubjectID	Date of Randomization	Randomized By
Mild	101	A				
Mild	102	A				
Mild	103	B				
Mild	104	B				
Mild	105	B				
Mild	106	A				
Mild	107	A				
Mild	108	B				

1.5 Study population:

Adult patients (18 years of age or older) who are hospitalized with a positive RT-PCR for SARS-CoV-2 within the last 14 days, with illness duration within the last 14 days, and evidence of moderate to severe COVID-19 infection as defined by NIH COVID-19 Severity Categorization (see the Appendix of study protocol):

- Moderate illness: Individuals who show evidence of lower respiratory disease during clinical assessment or imaging and who have saturation of oxygen $\text{SpO}_2 \geq 94\%$ on room air at sea level.
- Severe illness: Individuals who have $\text{SpO}_2 < 94\%$ on room air at sea level, a ratio of arterial partial pressure of oxygen to fraction of inspired oxygen ($\text{PaO}_2/\text{FiO}_2$) $< 300 \text{ mm Hg}$, respiratory frequency $> 30 \text{ breaths/min}$, or lung infiltrates $> 50\%$.

Inclusion Criteria

- Male or female 18 years of age or older at the time of enrollment.
- Patients hospitalized with a positive RT-PCR for SARS-CoV-2 within the last 14 days, with illness duration within the last 14 days, and evidence of moderate to severe COVID-19 infection as defined by NIH COVID-19 Severity Categorization (8):

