5.2 Primary efficacy outcome

The primary efficacy endpoint of this study is a binary indicator for whether a patient would be alive and free of invasive mechanical ventilation at 28 days. The outcome will be summarized as the proportion of patients alive and free of invasive mechanical ventilation at 28 days and the difference in the proportions between the two study arms will be evaluated with Chi-square test. The odds ratio of being alive and free of invasive mechanical ventilation at 28 days for Dupilumab vs. placebo and its 95% confidence interval (CI) will be estimated in logistic regression, adjusting for potential baseline characteristics if necessary.

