This trial is intended to be an early stage and proof of concept study with the primary goal to collect reliable data and obtain sufficient evidence for future trials. Thus, the emphasis of the study is an exploratory estimation of effect size and incidence of adverse events in terms of eosinophilia; it is not considered as a pivotal trial for efficacy at this time. Therefore, a larger significance level (one-sided alpha=0.1), and the sample size is pre-selected based on the feasibility. Given the current decline trend in the incidence of COVID-19 positive cases, we anticipate to enroll 40 patients realistically into this randomized clinical trial, which shall be sufficient for us to collect reliable and interpretable data for proof of concept to inform future trials. The COVID-19 hospitalization data from our University of Virginia Health System between March 2020 and April 6, 2021 showed that 79.5% of COVID-19 inpatients were alive and free of mechanical ventilation at 28 days under the usual care. With 40 patients that are deemed to be feasible, we would expect Dupilumab to improve a margin of 17.7% in the proportion of patients alive and free of mechanical ventilation at 28 days. That is, it is anticipated that 97.2% of patients being alive and free of ventilation at 28 days in the Dupilumab arm. The power analysis is conducted using the one-sided Score test (Farrington & Manning) with 75% power and 10% type I error.

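### For binary outcomes, the exploratory adjusted odds ratio in Protocol 6.1 is likely to be exaggerated, and sometimes not estimable, if the listed covariates enter an ordinary logistic model in at most 33 patients

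*Protocol*

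**What the plan says.** Protocol 6.1 compares the arms by Chi-square for categorical measures, naming the primary endpoint as an example, and by t-test or Wilcoxon test for continuous ones. It then adds that "the adjusted treatment effect of dupilumab will be estimated exploratively in generalized linear regression for the primary and secondary outcomes", the purpose being "to account for the potential impact of patient characteristics (e.g., age, sex, race and co-morbidities) and baseline biomarker measures". The patient characteristics are examples. The section does not give the number of terms, their coding or a selection rule. It names no penalised or exact method and does not say what happens if a model cannot be fitted. Protocol 7.1 names eight plasma biomarkers.

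Protocol 6.2 sets out "to assess the post recovery of remaining 33 patients from COVID-19", after 40 were enrolled and "7 of them died by Day 60". Protocol 4.2 excludes anyone "no longer alive, able or willing to complete follow up visit at 1 year after enrollment", so 33 is a ceiling. No event rate or power is stated for the follow-up.

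The SAP covers the parent trial. Its section 5.1 uses similar adjustment wording. Section 5.2 says the parent odds ratio "will be estimated in logistic regression, adjusting for potential baseline characteristics if necessary", with no rule for an arm without failures. On allocation, section 1.4 says "the blocked randomization with block size of 4 will be performed, stratifying based on disease severity", with strata of oxygen need at or below 15 L and above 15 L. That stratum is not among the example adjusters in Protocol 6.1 or SAP 5.1.

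**The concern.** Logistic regression by maximum likelihood is biased away from the null when there are few outcomes per model term. When some combination of terms predicts the outcome perfectly (separation), it has no finite solution. With 33 patients at most, a list of demographics, co-morbidities and biomarkers can reach that point quickly.

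The stakes lie in effect size, not in the main test. Protocol 6.1 says the purpose is to inform later trials. Beyond frequencies and percentages, the adjusted regression is the only treatment-effect estimate it specifies for binary outcomes. An exaggerated odds ratio carried into the next sample-size calculation would make that trial too small. An open covariate list also leaves the choice of model until after the data are seen.

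**Working it through.** **1. The plan's own figure.** The follow-up has none. The parent trial states 75% power (SAP 7.0: 40 patients 1:1, 79.5% v 97.2%, one-sided 10%, score test). Exact binomial enumeration with 20 per arm gives 75.1%, with actual type I error 9.85%. The parent inputs are therefore read correctly.

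**2. Outcomes available in the follow-up.** Assumptions not in the documents: 17 v 16 patients, true log odds ratio -1.0, placebo abnormal rate 50% or 30%.
- Placebo 50%: dupilumab odds = 1 × e^-1 = 0.368, so the rate is 0.368/1.368 = 0.269. Expected abnormal results = 16 × 0.50 + 17 × 0.269 = 12.6, or 12.6/8 = 1.6 per covariate with eight covariates.
- Placebo 30%: odds = 0.429 × 0.368 = 0.158, so the rate is 0.136. Expected = 16 × 0.30 + 17 × 0.136 = 7.1, or 0.9 per covariate.

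**3. Eight covariates, N=33.** Two separate simulations of this setting gave median maximum-likelihood log odds ratios of -1.30 to -1.47 and -1.40 to -1.48 for the true -1.0. On the odds-ratio scale that is about 0.23 to 0.27 against e^-1 = 0.37. The share of fits that failed was 11 to 38% in one and 8 to 33% in the other. The 38% belongs to the 30% placebo rate, with about 7 events. Firth fits gave medians of -0.90 to -0.99.

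**4. Sensitivity to model size and attendance.** A further simulation used 1,500 runs per setting, a true odds ratio of 0.33, covariates unrelated to outcome, and abnormal rates of 20%, 35% and 50%. Six slopes is a small reading of the list: arm, age, sex, race as two terms, one co-morbidity. Fourteen adds eight biomarkers.

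| N | Slopes | Less common outcomes per slope | Fits with separation (20/35/50% abnormal) | Median OR, other fits |
|---|---|---|---|---|
| 33 | 1 (arm) | 6.6–16.5 | 12 / 0.5 / 0.1% | 0.30–0.34 |
| 33 | 6 | 1.1–2.75 | 44 / 16 / 8% | about 0.26 |
| 33 | 14 | 0.5–1.2 | 85 / 53 / 42% | 0.12–0.17 |
| 25 (assumed) | 6 | 0.8–2.1 | 63 / 31 / 27% | 0.23–0.27 |
| 25 (assumed) | 14 | 0.4–0.9 | 98 / 94 / 91% | 0.14–0.26 |

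Since the covariates were unrelated to outcome, the exaggeration is small-sample bias, not confounding. Separation was counted for the whole model. Where only a covariate separates, the arm coefficient can stay finite, so these are shares of models that fail, not always of missing treatment effects.

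**5. Firth at the same model sizes.** At N=33 it converged in about 99 to 100% of runs, with median odds ratio 0.32 to 0.40 for every size from 1 to 14 slopes. The SD of the log odds ratio was 0.85 to 1.35 with 6 to 14 slopes. Even at 0.85, 1.96 × 0.85 = 1.67 and e^1.67 = 5.3, so the uncertainty is about five-fold each way.

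**6. Continuous outcomes.** A linear model with eight slopes leaves 33 - 8 - 1 = 24 residual degrees of freedom, so it can be estimated.

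**7. Parent trial, supporting only.** SAP 7.0 says "it is anticipated that 97.2% of patients being alive and free of ventilation at 28 days in the Dupilumab arm". P(no failures among 20) = 0.972^20 = 0.567. P(no failures on placebo) = 0.795^20 = 0.010. P(either) = 1 - 0.433 × 0.990 = 0.571. For 20/20 v 16/20 the ordinary odds ratio is infinite, while Firth gives (20.5 × 4.5)/(0.5 × 16.5) = 11.2.

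**The case against.** The main result does not use this model. The primary endpoint has an unadjusted Chi-square, the adjusted estimate is labelled exploratory, and Protocol 6.1 disclaims formal hypothesis testing. The covariates are examples, and nothing says that all enter together. The biomarker phrase may mean only the baseline value of the biomarker being analysed. The remark on small sample size can be read as explaining why the adjusted analysis is exploratory, not why adjustment is done. SAP 3.1 allows other methods where the data demand them, SAP 4.0 lists disease severity as a baseline characteristic, and SAP 5.2 permits adjustment for baseline characteristics, so the stratum is not ruled out.

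All of this stands, and it limits the point. It does not answer it. The SAP's allowance is generic and written for the parent trial, and nothing in Protocol 6.1 tells the analyst to keep the model small or what to do on separation. Even the six-slope reading is biased at N=33.

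Three stronger readings are tempting, and the documents do not support them:
- **Adjusted effects in general cannot be estimated.** This concerns binary outcomes only, and depends on event rate, number of terms and attendance.
- **Only one further covariate is tolerable.** Firth removed most of the bias at every model size tried at N=33, so the exact number is a judgement.
- **The parent odds ratio is bound to be infinite and SAP 5.2 must change.** The chance was 57% under the planning rates, a Chi-square test is planned beside it, and the Protocol reports the parent's enrolment closed and its 60-day results known.

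**Conclusion.** The point holds for the exploratory adjusted analysis of binary outcomes in Protocol 6.1. With eight covariates at N=33, ordinary logistic regression gives a median log odds ratio of about -1.3 to -1.5 for a true -1.0, and about 8 to 38% of fits fail. The problem is smaller with fewer terms and larger if attendance falls. These figures rest on assumed abnormal rates of 30 to 50% on placebo, a 17 v 16 split, assumed covariate distributions, joint entry of the terms, and maximum likelihood, which is inferred because no other method is named.

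A reader might infer that the study's primary comparison is compromised. It is not: the Chi-square does not depend on this model, and continuous outcomes remain estimable, though imprecise. The missing randomisation stratum is a separate, modest gap in the example list. The parent-trial figure illustrates the same weakness and calls for no action in this follow-up.

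**What to change.** In Protocol 6.1, for binary outcomes:
- Fit the exploratory adjusted model with Firth penalised likelihood and profile-likelihood intervals.
- Include the randomisation oxygen stratum (at or below 15 L v above 15 L).
- Keep other covariates to a short list, named with their coding before the follow-up data are analysed by arm.
- Report the unadjusted risk difference with a score-based 95% CI beside the Chi-square test, so that an effect size is available whatever happens to the model.

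The cost is a few sentences of protocol text and a different fitting option. SAP 3.4 names SAS 9.4, but no procedure for this model. Fewer covariates would be examined, and Firth makes the estimate finite without making it precise, so the text should say that wide intervals are expected.

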### 6.2 Sample Size justification

Under the protocol HSR 210184, we conducted a randomized double-blind placebo-controlled trial assessing the safety and efficacy of dupilumab for treating hospitalized patients with acute moderate to severe COVID-19, which was designed as an early stage (Phase IIa) and proof of concept study. A total of 40 patients were enrolled from June 23, 2021 through November 180 11, 2021 in the Phase IIa study, and 7 of them died by Day 60. The sample size of 40 in the original Phase II study were determined largely based on the feasibility with a primary goal to collection reliable data and obtain sufficient evidence for future trials. The current proposed study is an extension of the original Phase IIa study under the HSR 210184, to assess the post recovery of remaining 33 patients from COVID-19 with respect to pulmonary function testing (PFT), pulmonary imaging, immune biomarkers and symptoms at one-year follow-up. All data will be collected at a single visit, 1 year (i.e.,  $365 \pm 90$  days) after initial enrollment in the remaining 33 parents from the study HSR 210184. Formal sample size estimation and power analysis is not performed due to the pilot nature of this proposed follow-up study.

## 7.0 CLINICAL EFFICACY AND IMMUNE MEASURES

### 7.1 Clinical Efficacy

- Proportion of patients with abnormal diffusing capacity for carbon monoxide (DLCO) and/or 6 minute walk testing 1 year after acute COVID-19 infection
- Proportion of patients with new systemic, respiratory, musculoskeletal, neuropsychiatric and/or cardiac symptoms post COVID-19 consistent with long haul syndrome (fatigue, poor concentration, daily activity restriction, chronic malaise, asthenia, dyspnea, persistent cough, pleurisy, sleep abnormalities, chronic headache, olfactory impairments, gustatory impairments, brain fog, memory defects, depression, anxiety, dizziness, myalgias, joint pain, chest pain, palpitations): 1 year after HSR 210184 enrollment

- Proportion of patients with reduced neurocognitive function: 1 year after HSR 210184 enrollment
- Proportion of abnormal predicted forced expiratory volume (FEV1), forced vital capacity (FVC) and/or total lung capacity (TLC): 1 year after HSR 210184 enrollment
- Proportion of patients with new oxygen requirement after COVID-19 hospitalization: 1 year after initial enrollment
- Proportion of patients with greater than 3% oxygen desaturation during 6 minute walk testing: 1 year after HSR 210184 enrollment
- Plasma cytokine levels including TARC (CCL17), YKL40, eotaxin 3 (CCL26), IL-13, IL-4, Arg1, Hyaluronan, soluble ST2: 1 year after HSR 210184 enrollment
- Differences in high resolution computed tomography (HRCT) chest scan appearance post recovery: 1 year after HSR 210184 enrollment

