### Follow Up Visit on Day 365 $\pm$ 90 days after enrollment for HSR 210184 to discuss participation in 220171:

1. Urine pregnancy test at the time of consenting to rule out participation
2. Blood for immune evaluation of cytokine levels (1 light green top, 3 mL/draw)
3. CT chest imaging (non-contrast)
4. Pulmonary function testing (spirometry, lung volumes, diffusing capacity for carbon monoxide (DLCO), 6 minute walk testing (6MWT))
5. Symptom screen (fatigue, poor concentration, daily activity restriction, chronic malaise, asthenia, dyspnea, persistent cough, pleurisy, sleep abnormalities, chronic headache, olfactory impairments, gustatory impairments, brain fog, memory defects, depression, anxiety, dizziness, myalgias, joint pain, chest pain, palpitations)
6. Neurocognitive testing via questionnaire

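### The one-year neurocognitive endpoint is analysed only as reduced or not in at most 33 patients; if the questionnaire gives a graded score, comparing the score would estimate the effect more precisely

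*Protocol*

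**What the plan says.** Protocol section 7.1 lists the endpoint as "Proportion of patients with reduced neurocognitive function: 1 year after HSR 210184 enrollment", and the Secondary Endpoints in section 1.0 use the same wording. The visit schedule in section 5.0 gives the source as "Neurocognitive testing via questionnaire", an item separate from the symptom screen.

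Section 6.1 sets the test by type of measure: "tested with Chi-square for categorical measures (e.g., the primary endpoint) and two-sample t-test or Wilcoxon rank sum test for continuous measures (e.g., biomarkers". It also plans an exploratory generalized linear regression for the primary and secondary outcomes, with age among the example covariates.

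On numbers, section 6.2 says "A total of 40 patients were enrolled" in the parent trial and "7 of them died by Day 60". The extension is "to assess the post recovery of remaining 33 patients from COVID-19". Section 4.2 excludes parent-trial subjects "no longer alive, able or willing to complete follow up visit at 1 year after enrollment".

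The SAP is written for the parent trial. It lists no neurocognitive outcome and no analysis of one. No instrument, scoring rule or threshold for reduced function appears in either document.

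**The concern.** Because the endpoint is worded as a proportion, it falls under the chi-square rule. The regression in section 6.1 would also take the yes/no result as its outcome. A patient just below the cut counts the same as one far below it, and all patients above it count alike.

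In a study this small, that loss is hard to justify if a graded score has already been collected. Section 6.1 says the aim is to inform later trials. A proportion at an unstated cut gives neither a mean difference nor an SD with which to plan one.

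**Working it through.** **Available patients.** 40 enrolled − 7 deaths = 33, which reproduces section 6.2. This is an upper bound, because section 4.2 also removes later deaths and anyone unable or unwilling to attend. The plan states no power for this endpoint, so there is no power figure to reproduce.

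**Inputs from the documents.**
- Test family: chi-square, or t-test/Wilcoxon (protocol 6.1).
- Two-sided 5% level: SAP 3.4, written for the parent trial. Protocol section 6 gives no level.
- 1:1 randomisation: SAP 1.2 and 1.4.

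**Assumed inputs.**
- 16 placebo and 17 dupilumab patients, since survivors by arm are not given.
- A roughly normal score with equal SD in both arms.
- A standardised difference d of 0.5, 0.8 or 1.0 in favour of dupilumab.
- A placebo proportion reduced, p, of 50%, 40%, 30% or 20%.

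**Information kept by the cut.** For a normal score cut at c = Φ⁻¹(p), the relative efficiency of yes/no against the score is φ(c)² / [p(1 − p)].
- p = 50%: 0.3989² / 0.25 = 0.64, so 36% is lost.
- p = 30%: 0.3477² / 0.21 = 0.58, so 42% is lost.
- p = 20%: 0.2800² / 0.16 = 0.49, so 51% is lost.

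**Power as yes/no.** The dupilumab proportion is Φ(Φ⁻¹(p) − d). At d = 0.8 this gives 50% vs 21%, 40% vs 15%, 30% vs 9% and 20% vs 5%. Power is the exact binomial probability that the uncorrected two-sided chi-square rejects.

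**Power on the score.** This uses the noncentral t with 31 degrees of freedom and noncentrality d√(16 × 17 / 33) = 2.871d, with critical value 2.040. At d = 0.8 the noncentrality is 2.30. Wilcoxon power is simulated (6,000 runs).

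| d | Yes/no, p = 50% | 40% | 30% | 20% | t-test | Wilcoxon |
|---|---|---|---|---|---|---|
| 0.5 | 20% | 21% | 17% | 12% | 28% | 27% |
| 0.8 | 43% | 40% | 32% | 20% | 61% | 58% |
| 1.0 | 59% | 53% | 42% | 26% | 79% | 77% |

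A separate simulation of 20,000 trials per scenario agrees within about one or two points, with 27–29% on the score at d = 0.5. At zero effect its tests reject at 4.5–5.4%. A 14/19 split gives similar results at d = 0.8: 60% on the score against 43%, 34% and 26% for p = 50%, 30% and 20%.

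**Lower attendance, d = 0.8 (p = 50% / 30% / 20%).**
- 24 patients (12 per arm): 47% on the score vs 33% / 21% / 12%.
- 20 patients (10 per arm): 40% on the score vs 24% / 15% / 7%.

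**Ceiling, d = 0.8, 16 vs 17.** Wilcoxon power is 58% with no ceiling. It falls to 54%, 46% and 33% when 30%, 50% and 70% of placebo scores sit at the maximum. If that maximum coincides with the cut, the comparison becomes 46% vs 43% (50% cut) and 33% vs 32% (30% cut).

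**Precision of the score estimate.** The 95% interval half-width is 2.040 × √(1/16 + 1/17) = 0.71 SD with all 33 attending. It is 2.074 × √(1/12 + 1/12) = 0.85 SD with 24.

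**The case against.** The strongest objection is that the documents never say a score exists. The questionnaire could give a total, a few categories or item-level yes/no answers. This stands, and it makes the point conditional. The gap that holds whatever the instrument is that neither the instrument nor the meaning of *reduced* is stated.

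Second, the protocol disclaims formal testing and did no power analysis, so power is not its own yardstick. That is fair, and the power figures are best read as a measure of lost precision. It does not defend the yes/no form, because a study meant to inform later trials needs an effect estimate and an SD.

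Third, section 6.1 already provides methods for continuous measures, and biomarkers are only its example. True, but those methods apply to endpoints that are continuous, and no neurocognitive score is listed. What is missing is the endpoint, not the method.

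Fourth, a binary endpoint could count death as a bad outcome, whereas a score needs a rule. As written, the endpoint does not count death as reduced function, and section 4.2 excludes those who died. Moving to the score therefore gives up no existing protection, but deaths and non-attendance must be shown beside either form.

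A reader might go further and infer that the score would recover a large loss of power at no cost, or turn an uninformative comparison into an adequate one. The documents support neither. The size of the gain rests on assumed effects, cuts and score shape, and a score analysis at 0.5 SD has only about 28% power even with all 33 attending.

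**Conclusion.** The concern holds in a conditional form. The endpoint is defined only as a proportion, so it goes to chi-square in at most 33 patients, and no score analysis is listed in either document.

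If the questionnaire gives a numeric or ordered score that is roughly normal, the cut discards about 36–51% of the information for placebo proportions of 50% down to 20%. With 16 versus 17 patients, the power difference at 0.8 SD is about 18–41 points by t-test and slightly less by Wilcoxon. At 0.5 SD it is about 8–17 points. It is smaller with lower attendance and close to zero when a ceiling coincides with the cut.

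In none of the ceiling scenarios examined does the score do worse than the yes/no form. The gain is in precision and planning information; the comparison remains underpowered for moderate effects.

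**What to change.** In protocol sections 1.0 and 7.1:

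1. Name the neurocognitive instrument and define *reduced*, including the cut-off.
2. Where the instrument gives a graded score, make the between-arm comparison of that score at one year, among those assessed, the analysed form of this endpoint. Use the Wilcoxon test, with the between-arm difference and its 95% CI, and an exploratory linear model adjusted for age.
3. Keep the proportion with reduced function as a descriptive summary.
4. Report deaths and non-attenders by arm beside the result, because the score is seen only in survivors who attend.

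If the instrument gives no graded score, items 1 and 4 still apply and the proportion stays as the analysed form.

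The cost is protocol wording. The questionnaire is already scheduled and section 6.1 already contains the tests and the exploratory regression, so no extra visit or patient burden follows.
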